- (v) **Lower fat mass leads to altered levels of adipokines (lower leptin, higher adiponectin) and fat regulated hormones (higher ghrelin, PYY, cortisol)**
- (vi) **Altered levels of adipokines and fat regulated hormones determine a relative hypogonadal state**
- (vii) **Hypogonadism and altered levels of adipokines and fat regulated hormones have a deleterious effect on bone density, structure (assessed by HRpQCT) and estimated bone strength (using FEA)**
- (viii) **Higher visceral adipose tissue (assessed using MRI) and marrow fat (assessed using MRS) are associated with impaired bone density, structure and strength**

Specific Aim 8: We will test the hypothesis that in adolescent and young adult male athletes

- (i) **The impact of athletic energy deficit on gonadal status and bone density, structure and strength is less marked than in female athletes of comparable maturity**
- (ii) **The lesser impact of athletic energy deficit on gonadal status compared with female athletes is attributable to greater lean mass, a lower absolute reduction in fat mass than in females (given lower baseline fat in males than in females), and a lesser impact on adipokines and fat regulated hormones**
- (iii) **A lesser impact of athletic energy deficit on testosterone secretion in males (compared with amenorrhea and hypoestrogenism in females) causes greater preservation of lean mass in males and a lesser impact on bone than in females**

BACKGROUND AND SIGNIFICANCE

Provide a brief paragraph summarizing prior experience important for understanding the proposed study and procedures.

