Subjects will be 14-25 year old female athletes with AA (n= 145), EA (n=), and female non-athletic controls (n= 42). Because different kinds of physical activity have different effects on bone metabolism, we will enroll only endurance athletes (please see Inclusion Criteria).

For Specific Aims 7-8, 40 adolescent and young adult male athletes 14-21 years old, and 20 adolescent and young adult male non-athletes 14-21 years old will be studied. Eligibility will be assessed over the phone, and the study will include one visit only.

Participation of Children: We will enroll only female adolescents/young adults to optimize power and avoid issues arising from deficiencies of different predominant sex hormones in boys (testosterone) vs. girls (estrogen). Adolescents and young adults will be studied to determine effects on BMD and its predictors in a population that should be actively accruing bone.

Inclusion Criteria

(i) Females 14-25 years old: Our pilot data are reassuring in that young women 14-25 years old with hypothalamic amenorrhea are not adversely affected with estrogen use. In fact, in our prospective study, beneficial effects were observed both in young women 18-25 years old using oral estrogen, and in 14-18 year old adolescent girls using transdermal estrogen. We therefore feel that including girls in the 14-21 year age range will not be hazardous to their bone health. In fact, given the lack of data in this age group, it is important to study younger women and teenagers rather than extrapolate data from studies in adults to this younger population. Hormone dynamics differ in teenagers compared with adults, and bone mass accrual is even more dependent on estrogen and IGF-1 in younger than older women who have already achieved peak bone mass.

(ii) Bone age (BA) \geq 14 years: 98% of adult height is achieved at a BA of 14 because only 2% of growth potential persists at a BA of 14 years. Thus, to avoid potential stunting of growth potential with estrogen replacement, we have chosen to include girls with BA of \geq 14 years.

(iii) BMI between 10th-90th percentiles for age, or BMI of at least 85% of ideal BMI

(iv) Amenorrhea (for AA): absence of menses for \geq three months (74) within a period of oligomenorrhea (cycle length $>$ six weeks) for \geq six months, or absence of menarche at ≥ 16 years

(v) Eumenorrhea (EA and controls): \geq nine menses (cycle length 21-35 days) in preceding year.

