- (iii) Endurance athletes engaged in sports that involve weight bearing training of the legs. Severity of low BMD and gonadal dys-function may differ by type of exercise (131). By limiting enrollment to weight bearing endurance athletes, we will eliminate variability from type of activity. Endurance training is defined as \geq 4h of aerobic weight-bearing training of the legs or specific endurance training weekly, or \geq 20 miles of running weekly for \geq 6 months in the last year. Cyclists, rowers and swimmers will not be included because these activities do not involve lower extremity weight bearing. Gymnasts will not be included (not an endurance sport),
- (iv) Non-athletes will be eligible if weight bearing exercise activity is $<$ 2h a week and they are not participating in organized team sports.

Exclusion Criteria:

- (i) Use of medications affecting bone metabolism (washout period of 3 months prior to enrollment if medically permissible to discontinue these)
- (ii) Conditions other than endurance training that may cause hypogonadism or low bone density
- (iii) High TSH, FSH or prolactin
- (iv) Standard MRI exclusion criteria such as presence of pacemaker, intracranial metal clips, severe claustrophobia

Briefly describe study procedures. Include any local site restrictions, for example, "Subjects enrolled at Partners will not participate in the pharmacokinetic portion of the study." Describe study endpoints.

Over the proposed 5-year investigation, 145 teenage girls and young adults 14-25 years old with AA, 42 EA and 42 non-athletic controls will be studied. Eligibility will be assessed at the screen, and the study will include a baseline visit and follow up visits at 3, 6, 9 and 12 months. The baseline visit will occur within 8 weeks of the screen. EA and controls will be followed without intervention (except elemental calcium and vitamin D) for 12 months.

For Specific Aim 3 we anticipate screening 2 times the number of athletes that we will eventually enroll in the study to obtain 145 eligible AA adolescents. In addition, for Specific Aims 1 and 2, we anticipate screening 2 times the number of EA (n=42) and non-athletic controls (n=42) required for this section of the study (total subjects to be screened= 458).

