- (b) Fasting (or 2 hour post-prandial) blood samples for IGF-1, estradiol, testosterone, SHBG and LH, bone turnover markers (PINP and N-telopeptide).

Male Study Visit:

- (a) History and physical exam (H&P)
- (b) 7-8 AM Hormones: TSH, FSH, LH, testosterone, SHBG, estradiol, IGF-1, leptin, ghrelin (total), PYY (total),
- (c) 11 PM salivary cortisol (to be mailed back);

- (d) Calcitropic Measures and Markers of Bone Turnover: calcium, phosphorus, 25(OH) vitamin D, 1,25(OH)₂ vitamin D, PTH; PINP and CTX.
- (e) Activity Assessment: Bouchard 3-day activity record (129). Habitual activity will be further assessed using a standardized exercise questionnaire, which provides a good estimate of past year physical activity (173, 199),
- (f) 4-day food diary to assess caloric intake (NDS, version 4, Minneapolis, MN) and determine standard macronutrient intake,
- (g) Eating disorder questionnaire (EDI-2) (186), Three-Factor Eating Questionnaire-R18 (TFEQ),
- (h) Resting energy expenditure (REE) using indirect calorimetry,
- (i) VO₂ max and handgrip strength,
- (j) BMD: Lumbar spine, hip, radius, whole body areal BMD will be measured by DXA,
- (k) Body Composition: Whole body DXA will be used to assess fat and lean mass. In a subset of 10 athletes and 10 non-athletes, we will use MRI to assess SAT, VAT, thigh muscle area and marrow fat, (198) Bone microarchitecture and strength will be determined at the ultradistal radius and distal tibia using HR-pQCT (Xtreme CT, Scanco Medical AG). Bone strength will be determined using FEA of HR-pQCT scan data (187).

DNA testing:

We may ask subjects to participate in DNA testing via a saliva collection and/or blood collection at some point during this study in order to determine if there is a genetic basis for the hormonal changes seen in non-menstruating athletes. During one of the 6 visits for the “Fat Mediated Modulation of Reproductive and Endocrine Function in Young Athletes” study, we may draw 50cc (slightly more than 3 tablespoons) of blood for DNA testing, and may also ask for a sample of saliva for DNA testing. This will be an optional portion of the study, with a separate section of the consent forms to address this.

MRI:

We would like to assess SAT, VAT, thigh muscle area and marrow fat of AA prior to treatment and EA and non-athlete controls at some point during their 1 year study enrollment using MRI.

Finite Element Analysis:

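### The male visit lists no adiponectin assay, although Aim 7(v) tests it, and no prolactin assay, although high prolactin is a male exclusion

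*Protocol*

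**What the plan says.** Specific Aim 7(v) of the Protocol states the hypothesis for male athletes: "Lower fat mass leads to altered levels of adipokines (lower leptin, higher adiponectin) and fat regulated hormones (higher ghrelin, PYY, cortisol"). Aim 7(vi) builds on it: "Altered levels of adipokines and fat regulated hormones determine a relative hypogonadal state". Aim 7(vii) carries adipokines and fat-regulated hormones on to bone outcomes. Aim 8(ii) attributes the smaller gonadal effect in males partly to a smaller effect on adipokines than in females.

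The male exclusion criteria include, as item (iii), "High TSH, FSH or prolactin".

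On scheduling, Research Design and Methods says of the males: "Eligibility will be assessed over the phone, and the study will include one visit only".

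The assays at that visit are listed under Male Study Visit:
- item (b), drawn at 7-8 AM: "TSH, FSH, LH, testosterone, SHBG, estradiol, IGF-1, leptin, ghrelin (total), PYY (total");
- item (c): "11 PM salivary cortisol (to be mailed back");
- item (d): "calcium, phosphorus, 25(OH) vitamin D, 1,25(OH)₂ vitamin D, PTH; PINP and CTX".

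For females, adiponectin is named in the blood panels at baseline and at the 6- and 12-month visits, on fasting or 2-hour post-prandial samples. The SAP says nothing about assays in males.

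**The concern.** The aims, the eligibility criteria and the procedures for the males do not agree.

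First, a stated hypothesis names an analyte that the visit does not measure. Adiponectin is one of only two adipokines named in Aim 7(v). If the visit is run as listed, that part of the aim cannot be tested in males, and adiponectin values will exist for females only when the sexes are compared.

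Second, a laboratory exclusion has no scheduled test. Aims 7 and 8 ask whether athletic energy deficit lowers gonadal function in males. Male exclusion (ii) shows that the Protocol wants other causes of hypogonadism kept out. A male with unrecognised high prolactin would pass through the plan as written, and any low testosterone he had could be counted as an effect of training.

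**Working it through.** No sample size, power or error-rate figure bears on this point, so the check sets the passages side by side and counts coverage.

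**Step 1. Markers in Aim 7(v) against the male assay lists**

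| Marker in Aim 7(v) | Measured at the Male Study Visit? |
|---|---|
| Leptin | Yes, item (b) |
| Adiponectin | No |
| Ghrelin | Yes, item (b), total |
| PYY | Yes, item (b), total |
| Cortisol | Yes, item (c), salivary |

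Coverage is 4 of 5. The missing marker is one of the two adipokines.

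**Step 2. Laboratory values in male exclusion (iii) against the same lists**

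| Value in exclusion (iii) | Measured at the Male Study Visit? |
|---|---|
| TSH | Yes, item (b) |
| FSH | Yes, item (b) |
| Prolactin | No |

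Coverage is 2 of 3.

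**Step 3. Could another scheduled sample supply the missing values?**

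- Item (d) of the male visit covers mineral metabolism and bone turnover only.
- The in-person Screening Visit has a laboratory list and a 30 cc sample frozen for later analysis. Males do not have that visit, because they are screened by phone, and its list does not include prolactin in any case.
- Prolactin appears once in the two documents, in the male exclusion itself. It is in no laboratory list for either sex.
- Adiponectin is listed only in the female panels.

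**Step 4. Is this an artefact of the extracted text?** The item (b) list ends in a comma after PYY, which might suggest that a further analyte was lost. Several other items in the same list, (e) to (j), also end in commas, so the comma is no evidence of that.

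**Step 5. Numbers affected.** 40 male athletes + 20 male non-athletes = 60. No adiponectin measurement and no prolactin measurement is planned in any of the 60.

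**Step 6. Timing of the exclusion.** TSH and FSH are on the panel, but eligibility is settled by phone before any blood is taken. All three values in exclusion (iii) could therefore be known only after the single visit. The Protocol does not say what happens to a male whose result is then out of range.

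**The case against.** Several points can fairly be made on the other side.

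- *The prolactin exclusion can still operate.* A reader might infer that the criterion cannot be applied at all, or that prolactin status would be unknown in every male. The documents do not support that. The phone screen and the history and physical examination could identify a known diagnosis, and exclusion (ii) separately bars other causes of hypogonadism. The gap concerns undiagnosed high prolactin.
- *Affected males may not exist.* The documents give no prevalence of high prolactin in this population, so no bias can be calculated. The plan allows such males to remain; it does not show that any would.
- *Samples may be available.* The Specimens paragraph under Monitoring and Quality Assurance says that most study-visit blood is frozen and stored, and the recruitment section allows a month for running male samples for secondary endpoints and for data analysis. Later assay may therefore be possible. Neither place names adiponectin or prolactin, so the measurement remains unplanned, but it would be too strong to say that the data can never exist.
- *The wider aims survive.* A reader might infer that Aims 7(vi), 7(vii) and 8(ii) fail as well. They refer to adipokines and fat-regulated hormones in general and do not name adiponectin. They remain testable with leptin, ghrelin, PYY and cortisol.
- *The main trial is untouched.* The SAP's primary endpoint and power calculation concern randomized amenorrheic females. Aims 7 and 8 are a one-visit observational addition.

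These points limit the reach of the finding. They do not remove the mismatch, because followed as written the plan still tests a marker that it does not measure and excludes on a laboratory value that it does not obtain.

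**Conclusion.** The point holds in a limited form. No adiponectin or prolactin assay is listed for males, which conflicts with Aim 7(v) and with male exclusion (iii). One of the five Aim 7(v) markers has no planned measurement in the 60 males, so adiponectin has no male side in the Aim 8(ii) comparison. Undiagnosed high prolactin would go undetected, and affected males could remain in the Aim 7-8 analysis. The size of any resulting bias is unknown.

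This rests on two assumptions: that the Male Study Visit list is the complete set of male assays, and that males have no blood draw outside that visit. Nothing in either document contradicts them.

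The mismatch is worth correcting before males are studied, because one visit leaves no later scheduled draw. It gives no reason to question the randomized comparison or its sample size.

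**What to change.** 1. **Adiponectin.** Add it to the 7-8 AM male draw, or state that it will be run on stored male samples. Use the assay used for females. Record fasting status in males so that sampling can be matched to the female fasting or 2-hour post-prandial samples; the male list gives only a clock time. If the assay will not be run, remove adiponectin from Aim 7(v).
2. **Prolactin.** Reconcile exclusion (iii) with the panel by adding prolactin to the same draw. Deleting prolactin from the exclusions would make the text consistent, but would leave another possible cause of low gonadal function in the analysis.
3. **Analysis set.** State that males found after the single visit to meet the TSH, FSH or prolactin exclusion are left out of the Aim 7-8 analysis set, and report how many there were. This rule is needed for TSH and FSH even without prolactin.

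The cost is two assays in 60 males, which is 2 × 60 = 120 determinations, and possibly a few fewer males analysed. No extra visit is needed. The Protocol does not state the volume of blood drawn from males, so the sponsor should confirm that it is sufficient.

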STATISTICAL ANALYSIS PLAN

Title: Fat Mediated Modulation of Reproductive and Endocrine Function in Young Athletes

NCT00946192

Version Date: December 4, 2014

Statistical Analysis Plan

Biostatistical analysis: [name]., a collaborator on this grant, is our CRC statistician and has co-authored many papers with us and other members of the endocrine division. [name] and [name], Head of the Biostatistics Core, have been instrumental in study design and power analysis. [name] will also analyze the data at study completion. Analysis and interpretation of specific sub-aims are included in each section of the grant. Data generated will be largely longitudinal. Measures of hormone function, bone turnover, nutrition, activity and body composition will be collected every 6 months. In addition, there will be baseline variables. Subject groups include: AA randomized to transdermal estrogen, AA randomized to oral estrogen, AA randomized to observation, EA and controls. Randomization will be performed centrally by our research pharmacy.

The first step in data analysis is to determine models for longitudinal data collected. These models are usually based on our knowledge of how these data behave and details of the study. These models can also be checked to see whether they fit the data by viewing data for each patient without regard to patient group. For instance, BMD can be assumed to increase linearly over the study duration. We hypothesize that this linear increase will be slowest in untreated AA patients and intermediate in those on oral estrogen, and the smallest effect size would be the difference between groups randomized to transdermal versus oral estrogen. We would check this linearity by looking at data from individual patients and checking that actual measurements are normally distributed around the patient's linear trajectory by looking at residuals (difference between observed value and trend line). It is possible that in some cases linearity and normality might hold after a log or other transformation. If linearity holds for actual or transformed values, variables will be analyzed by mixed model ANOVA, a common method for analyzing longitudinal data. One advantage of this method is that it allows us to use data from subjects that drop out early. The linear model is appropriate for BMD, but will not be appropriate for variables that may be relatively constant during treatment. These might include measurements of bone turnover and hormones. These would be modeled assuming that each patient has a constant level. After examining how well the assumed model fits the data, repeated measures ANOVA will be used for analysis. In this model there is a fixed treatment term of primary interest. Measurements at each time are assumed to be a multivariate observation with an unspecified variance covariance matrix.

Power calculation for primary endpoint: Power analysis is based on the primary endpoint, i.e. average change in BMD over one year in a randomized trial comparing mean change in spine BMD in young women 14-25 years old with AA randomized to transdermal estrogen versus oral estrogen or no therapy for one year. Girls with AA will be stratified based on spine BMD Z-scores (≤ -1 or > -1).

Our preliminary data indicate a relative increase in spine BMD of 4.7% over one year with transdermal estrogen vs. no therapy. In addition, one study in AA women has reported a 1.5% relative increase in BMD in AA women following oral estrogen vs. placebo. Our preliminary data indicate that the SD for change in lumbar BMD over a year is 2.7%. Based on these data, using the Dunnett's test, a total of 99 AA (33 each in the two treatment arms no-treatment arm) will be needed to detect a difference of 3.2% (4.7%-1.5%) in mean %increase in spine BMD in groups receiving transdermal vs. oral estrogen, with a power of 80%, using a two sided $p=0.05$ level test.

The estimated sample size of 99 subjects with AA does not take into account study drop-outs. Based on previous studies, we expect an 8- 10% drop-out rate over one year. We thus estimate that we will need to recruit 109 subjects with AA (37 in the transdermal estrogen arm, and 36 each in the oral estrogen and no-treatment arms) to have 99 evaluable subjects at the end of the study. An independent Data and Safety Monitoring Board (consisting of an adolescent medicine physician, a statistician, a bone

expert, a pediatric endocrinologist and a psychiatrist) will review data regarding adverse events, study deviations and violations at study initiation and every six months. BMD information will be presented to the DSMB at each meeting, and study termination considered for subjects demonstrating >10% decrease in spine BMD from baseline, if randomized to estrogen.

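### The SAP calls transdermal versus oral (3.2%) the smallest effect, but its own inputs make oral versus no therapy (1.5%) the smallest, and no power is stated for it

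*SAP*

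**What the plan says.** The SAP's biostatistical analysis section sets out an expected ordering of BMD gain across the three randomized arms: untreated AA lowest, oral estrogen in between, transdermal highest. The same sentence adds that "the smallest effect size would be the difference between groups randomized to transdermal versus oral estrogen".

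The SAP's paragraphs on power for the primary endpoint then give the inputs:

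- Transdermal versus no therapy: "Our preliminary data indicate a relative increase in spine BMD of 4.7% over one year with transdermal estrogen vs. no therapy".
- Oral: "one study in AA women has reported a 1.5% relative increase in BMD in AA women following oral estrogen vs. placebo".
- Sizing contrast: the trial is planned "to detect a difference of 3.2% (4.7%-1.5%) in mean %increase in spine BMD in groups receiving transdermal vs. oral estrogen". The target is 80% power at the two-sided 5% level.
- Variability: "the SD for change in lumbar BMD over a year is 2.7" percent.

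The result is 99 evaluable AA, 33 per arm, using Dunnett's test. The SAP does not name the reference arm for that test and gives no power for oral versus no therapy. Specific Aim 3 in the protocol and the SAP's primary endpoint both set transdermal against the other two arms.

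**The concern.** An ordering of three arms contains three pairwise differences, and the lower step is oral versus untreated. By subtracting 1.5% from 4.7%, the SAP puts the 1.5% on the no-therapy scale and so uses it as oral versus none. On that footing oral versus none is the smallest difference, less than half the size of the one the SAP calls smallest.

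A trial sized on its smallest effect is normally taken to be adequate for the larger ones. A reader who accepts the sentence would suppose that oral versus none is covered, when no power for it has been worked out. If the assumed 1.5% benefit is real, the trial could still easily return a non-significant oral-versus-none result. The protocol's Expected Benefits section already describes oral estrogen as ineffective for BMD in adult AA, so such a result would be easy to over-read as confirmation.

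**Working it through.** **Inputs.** All are from the SAP's power section unless marked: transdermal minus none 4.7%; oral minus none 1.5% (reported against placebo in another study, used by the SAP against no therapy); SD of one-year change 2.7%; 33 evaluable per arm; two-sided 0.05; Dunnett's test with two comparisons; loss 8–10%. The protocol's Research Design and Methods section gives 145 AA to be enrolled, whereas the SAP plans to recruit 109.

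**Step 1. The three differences.**
- Transdermal − none = 4.7%
- Transdermal − oral = 4.7 − 1.5 = 3.2%
- Oral − none = 1.5%

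The smallest is oral − none; 1.5/3.2 = 0.47.

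**Step 2. The SAP's own figure.** With equal arms, SE of a difference = 2.7 × √(2/n), and power comes from the noncentral t with noncentrality difference/SE. The Dunnett calculation uses pooled df = 3n − 3 and a simulated critical value; the unadjusted one uses the two-sample t with df = 2n − 2.

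For 3.2%:
- Unadjusted: power is 79.2% at n = 12 and 82.6% at n = 13.
- Dunnett: power is about 79.7% at n = 14 and 82.7% at n = 15, so 15 per arm (45 in total) are enough.
- At n = 33: SE = 2.7 × √(2/33) = 0.665, noncentrality = 3.2/0.665 = 4.81, and power is 99.7% unadjusted or 99.4% with Dunnett.

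The stated 33 per arm for 80% power does not reproduce. With Dunnett, 33 per arm would match 80% power if the SD were about 4.2% or the difference about 2.05%. The dropout step does reproduce: 99/(1 − d) gives 108 to 110 for d = 8–10%, against 109 stated.

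**Step 3. Power for oral versus none (1.5%).** The Dunnett column applies only if no treatment is the reference arm.

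| Evaluable per arm | SE | 1.5/SE | Unadjusted t | Dunnett |
|---|---|---|---|---|
| 33 (SAP) | 0.665 | 2.26 | 60.4% (critical value 1.998) | 50.7% (critical value about 2.245) |
| 43 (protocol's 145) | 0.582 | 2.58 | 72.1% (critical value 1.989) | 63.3% (critical value about 2.24) |

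The 43 assumes equal arms and 10% loss: 145 × 0.90/3 = 43.5. At 8% loss, 145 × 0.92/3 = 44.5; with 44 per arm, power is 73.1% unadjusted and 64.4% with Dunnett. Reaching 80% for 1.5% would need 52 per arm unadjusted, or 62 with Dunnett.

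**Step 4. Precision.** The unadjusted 95% CI half-width for oral minus none is 1.998 × 0.665 = 1.33 points at 33 per arm and 1.989 × 0.582 = 1.16 points at 43 per arm.

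**The case against.** The strongest reply is that the sentence is true of the contrasts the trial means to test. Specific Aim 3, the protocol's background section and the SAP's primary endpoint all compare transdermal with oral and with no treatment. Dunnett's test compares several arms with one reference, and the SAP applies it to transdermal versus oral, so a consistent reading makes transdermal the reference. The tested contrasts are then 3.2% and 4.7%, and 3.2% is the smaller. Oral versus none is nowhere named as primary, and modest power for a non-primary comparison is ordinary in a three-arm trial.

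Most of this stands, and it is why the point is minor. It does not make the sentence correct as written. The sentence carries no restriction to transdermal contrasts, it directly follows an ordering that includes oral versus untreated, and the reference arm is never named. In the common set-up with no treatment as reference, oral versus none would be one of the two tested contrasts, and the contrast used for sizing would fall outside the Dunnett family.

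Two stronger readings are tempting, and the documents support neither:

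- **That the SAP promises at least 80% power for every contrast.** It attaches 80% to transdermal versus oral only.
- **That the investigators plan to read a null oral result as no effect.** The Expected Benefits wording describes earlier evidence in adults, and the SAP lays down no such interpretation.

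**Conclusion.** The concern holds in a limited form. Taken across all three arms, the smallest-effect statement conflicts with the SAP's own inputs. Oral versus none at 1.5% is the smallest difference, and its power is below 80% under either document's enrolment figure: about 60% unadjusted at 33 per arm and 72% at 43, or 51% and 63% if no treatment is the Dunnett reference.

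These figures rest on the SAP's 1.5% and 2.7%, on carrying a placebo-based difference over to an untreated arm as the SAP does, and, for 43 per arm, on equal allocation and 10% loss. They are also only as good as a set of inputs that does not reproduce the SAP's own sample size.

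Severity is minor. On the stated inputs the two transdermal contrasts have over 99% power at 33 per arm, so the primary comparison, the sample size and the main conclusion do not change.

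**What to change.** 1. Reword the sentence in the SAP's biostatistical analysis section: 3.2% is the smaller of the two contrasts with transdermal, and oral versus no therapy, at 1.5%, is the smallest of the three.
2. Name transdermal as the Dunnett reference arm, in line with Specific Aim 3 and the primary endpoint.
3. State the power for oral versus none (about 60% unadjusted at 33 per arm) and list the contrast as secondary. Report it as an estimate with a 95% CI, half-width about 1.3 points at 33 per arm, and say that non-significance will not be read as absence of an oral effect.
4. Separately, recheck the sample-size calculation. As stated, 3.2% with SD 2.7% needs about 15 per arm for 80% power with Dunnett. If the effect, SD or N changes, restate the power in item 3 to match, using whichever of the SAP's 109 and the protocol's 145 is confirmed.

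Items 1 to 3 cost a few lines of SAP text and one less favourable stated power. They need no extra participants and no change to the primary analysis.

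### The SAP does not say how the baseline hormone and bone-marker values are used, and no model names the randomisation strata; stating both for the randomised AA arms is a cheap, low-priority gain in precision.

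*SAP*

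**What the plan says.** **Hormones and bone markers.** The SAP (Statistical Analysis Plan section) sets these apart from BMD as "variables that may be relatively constant during treatment". It continues: "These would be modeled assuming that each patient has a constant level", then repeated-measures ANOVA with an unstructured covariance, in which "In this model there is a fixed treatment term of primary interest". The SAP's other reference to baseline is one line after the list of longitudinal measures: "In addition, there will be baseline variables". No use is given.

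**What is drawn.** Protocol, Baseline Study Visit item (e), takes the full hormone and marker panel before treatment, and the 6- and 12-month visits repeat it. The 3- and 9-month visits, item (b), repeat only IGF-1, estradiol, testosterone, SHBG, LH and the two bone markers. The SAP describes collection as six-monthly and does not mention the extra draws.

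**BMD.** If linearity holds, "variables will be analyzed by mixed model ANOVA, a common method for analyzing longitudinal data".

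**Strata.** Protocol, Screening Visit item (e), stratifies AA by spine Z-score (at or below -1, or above) and gives dancers their own randomisation template. The SAP mentions the first once, under the power calculation ("Girls with AA will be stratified based on spine BMD Z-scores"), and never mentions dancers. Neither factor appears in a model.

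**The concern.** A pre-treatment value of the outcome is usually the best available predictor of its later values, and here it costs nothing because it is already drawn. As written, two analysts could fit different models. One would leave baseline out and lose precision. Another would count baseline among the repeated measurements; with a single constant treatment term, that averages a visit with no treatment effect into the estimate.

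IGF-1 is among the affected outcomes. Protocol, Background and Significance, gives its sparing as the reason to expect transdermal to outperform oral estrogen. Bone markers have no such stated role but share the model.

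Factors used to balance the allocation would normally also enter the analysis. Leaving them out makes the model-based standard error too large whenever they predict the outcome.

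**Working it through.** **1. The plan's own figure.** The SAP powers only spine BMD change: difference 3.2 points (4.7 - 1.5), SD 2.7, 33 evaluable per arm, two-sided 5%, Dunnett, 80% power. The standard error of a pairwise difference is 2.7 × √(2/33) = 0.665, and 3.2/0.665 = 4.81. Power is therefore 99.7% at an ordinary two-sided 5% level and 99.4% at a Dunnett critical value of 2.245. The 33 per arm does not reproduce as an 80% design: the normal formula 2 × (1.96 + 0.842)² × (2.7/3.2)² gives 11.2, so 12 per arm, and Dunnett needs 14-15. That is a separate matter; here it shows only that primary power has slack. The SAP gives no such figure for hormones or markers.

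**2. Baseline unused against baseline adjusted.** Assume unit variance, *k* follow-up visits and equal correlation ρ between all visits. The range of ρ is an assumption.

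- Variance of the follow-up mean, baseline unused: v = (1 + (k-1)ρ)/k
- Variance with baseline as covariate: v - ρ²
- SE ratio: √(v/(v - ρ²))
- Sample size per arm that would do as well with adjustment: 33 × (v - ρ²)/v

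| k | ρ | v | v - ρ² | SE ratio | 33 per arm is worth |
|---|---|---|---|---|---|
| 2 | 0.3 | 0.650 | 0.560 | 1.077 | 28.4 |
| 2 | 0.5 | 0.750 | 0.500 | 1.225 | 22.0 |
| 2 | 0.7 | 0.850 | 0.360 | 1.537 | 14.0 |
| 4 | 0.3 | 0.475 | 0.385 | 1.111 | 26.7 |
| 4 | 0.5 | 0.625 | 0.375 | 1.291 | 19.8 |
| 4 | 0.7 | 0.775 | 0.285 | 1.649 | 12.1 |

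The k = 4 rows apply only to analytes drawn at months 3 and 9, and only if those draws are used. Leptin, adiponectin, ghrelin, PYY, insulin and FSH have k = 2.

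If correlation instead decays with distance (first-order autoregressive, adjacent-visit ρ of 0.3 / 0.5 / 0.7), the variance of the generalised least squares mean is 1/(1ᵀV⁻¹1). V is the follow-up covariance matrix, reduced by ccᵀ when baseline is adjusted for, where c holds the covariances with baseline. For k = 2 the variances are 0.650 / 0.750 / 0.850 unused and 0.611 / 0.600 / 0.468 adjusted, so the SE ratios are 1.032 / 1.118 / 1.348. For k = 4 they are 0.382 / 0.500 / 0.654 and 0.368 / 0.429 / 0.402, with ratios 1.019 / 1.080 / 1.276. Over both structures the SE loss runs from 2% to 65%.

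**3. Baseline as a response.** Under equal correlation a constant treatment term weights all k + 1 visits equally, and baseline carries no effect. The estimate is k/(k + 1) of the true effect: 2/3 = 67% or 4/5 = 80%.

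**4. Strata omitted from the BMD model.** Let R² be the share of variance in 12-month change that the strata explain (assumed; not in the documents). The interval is too wide by 1/√(1 - R²), and the true type I error is 2Φ(-1.96/√(1 - R²)).

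| R² | Width ratio | True type I error | Half-width with strata fitted |
|---|---|---|---|
| 0 | 1.00 | 5.0% | 1.32 points |
| 0.05 | 1.03 | 4.4% | 1.29 |
| 0.10 | 1.05 | 3.9% | 1.25 |
| 0.20 | 1.12 | 2.8% | 1.18 |

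Without the strata the half-width is 1.32 throughout. In simulation, a stratum that shifted BMD level by 15 points but not slope gave a width ratio of 1.000.

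**5. Cost if the covariates are noise.** With 99 subjects, 3 arms and p covariates, variance rises by a factor 1 + p/(99 - 3 - p - 1): 1.1%, 2.2% and 3.3% for p = 1, 2, 3. Baseline alone pays for itself at a correlation of no more than about 0.10.

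**6. Why the adjustment must stop at the randomised arms.** Under equal correlation the slope of follow-up on baseline is ρ. A stable 1 SD difference between non-randomised groups therefore shrinks to 1 - ρ after baseline adjustment: 0.7 / 0.5 / 0.3 SD at ρ = 0.3 / 0.5 / 0.7.

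**The case against.** The strongest reply is that the SAP never says treatment is the only term: calling it the term of main interest leaves room for others. The SAP also states that "Analysis and interpretation of specific sub-aims are included in each section of the grant", and the grant, which was not supplied, may list covariates. This stands. What can be said is that the SAP as supplied leaves the role of baseline unstated, not that baseline will go unused. If the grant settles it, the remedy is to copy the text across.

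A reader might infer that baseline is certainly discarded, because the outcomes are described as stable while on treatment and baseline variables are mentioned separately. The documents do not support that as a finding. The separate mention could equally mean items measured only once, such as bone age, with the baseline hormone draw inside the longitudinal series. Both readings stay open, so the 2-65% loss and the 67-80% dilution are alternatives.

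It is also fair that hormones and markers are not named outcomes of the randomised comparison in Specific Aims 3 and 6, and that IGF-1 appears as rationale only. This lowers the priority.

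On the strata, no document says that either predicts the rate of BMD change. Inclusion Criterion (vii) links type of activity to severity of low BMD, which concerns level.

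The SAP also has model fit checked by "viewing data for each patient without regard to patient group". That is a sound safeguard against choosing a model by its result, but it does not settle what baseline is for.

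The 3- and 9-month visits are labelled as abbreviated safety visits and the SAP speaks of six-monthly collection, so leaving those draws out is a natural reading. That part needs only a clarifying sentence.

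**Conclusion.** The gap is real but small: a low-priority improvement in precision, not a validity error. In the SAP as supplied, the hormone and marker model gives the baseline value no stated role, and no model names the Z-score strata or the dancer template.

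If baseline is unused, the randomised contrast is unbiased with an SE about 2-65% larger than it need be. That range rests wholly on the assumed correlation of 0.3-0.7, its structure and the number of visits. If baseline is a response under a constant treatment term, the effect is diluted to about 67% or 80%, given equal correlation.

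A reader might go further and infer that the primary result is biased or underpowered. It is not: omitting strata that were balanced by design leaves the BMD contrast unbiased and at most conservative, and power at the SAP's inputs exceeds 99%. A reader might also infer that baseline adjustment should apply to all five groups the SAP lists. It should not, because EA and controls were not randomised, have no randomisation strata, and are expected to differ from AA at the outset.

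**What to change.** For the comparison of the three randomised AA arms only:

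- **Hormones and bone markers:** use post-baseline values as the responses, with the baseline value, Z-score stratum and dancer status as covariates. Add one sentence on whether the month 3 and 9 samples enter.
- **BMD:** add Z-score stratum and dancer status, each with its time interaction, to the mixed model. Baseline BMD can remain the time-zero point of the trajectory.
- **Sparse dancer cells:** set a rule in advance and blind to arm, such as keeping only the Z-score stratum if fewer than a stated number of dancers are randomised. The number is a judgement; the documents do not say how many dancers are expected.

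State that the baseline and strata adjustments do not apply to comparisons with EA or controls. If the grant already lists covariates, transcribe them instead.

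The cost is SAP wording and a few degrees of freedom, about 1-3% in variance if the covariates turn out uninformative. No new data are needed.
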